8.2.1 General Assessments

8.2.1.1 Informed Consent

All subjects must sign and personally date the IRB/IEC approved informed consent before any study-specific procedures are performed.

8.2.1.2 Demographics

Demographic data collection including sex, age, race, and ethnicity will be collected in order to study their possible association with subject safety and treatment effectiveness. Additionally, demographic data will be used to study the impact on biomarkers variability and pharmacokinetics (PK) of the protocol-required therapies.

8.2.1.3 Medical History

The Investigator or designee will collect a complete medical history that started or was ongoing within 6 months prior to enrollment through day 1. Medical history will include information on the subject's concurrent medical conditions. In addition to the medical history above, the following should be collected back to the date of original diagnosis:

- cardiovascular history, including details of atherosclerotic cardiovascular disease and elevated Lp(a)
- history of cancer and/or malignancy
- history of immunologic or chronic inflammatory disease
- history of hepatobiliary dysfunction (including asymptomatic and/or transient liver function test abnormalities)
- history of renal disorder or abnormal renal findings
- history of non-stroke related neurological findings (eg, peripheral neuropathy)
- history of platelet disorder or coagulopathy
- diabetes mellitus history including, but not limited to, duration and complications (eg, acute metabolic complications, retinopathy, neuropathy)
- familial history of diabetes mellitus
- familial history of cardiac disorder

Record all findings on the medical history CRF. The current severity will be collected for each condition that has not resolved.

8.2.1.4 Physical Examination

Physical examination will be performed as per standard of care. Physical examination findings should be recorded on the appropriate CRF (eg, medical history, event).

8.2.1.4.1 Neurological and Muscular Examination

The clinical neurologic musculoskeletal examination will be performed to assess signs of new onset peripheral neuropathy or myopathy. The examination should be reported in the subject records and must include the following assessments:

- muscle mass and tone, presence of tremor, fasciculation or paralysis
- strength in all extremities, including proximal and distal muscular groups
- gait, by observation of a short regular walk, heel and toe walk
- symmetry of sensitivity to pressure (dull tool), temperature and pain (sharp tool)
- proprioception in upper and lower extremities
- symmetry of reflexes assessed on the upper extremities (biceps, triceps and brachioradial) and lower extremities (patellar and achilles)

If there is clinical evidence of treatment-emergent neuropathy or myopathy, dosing will be suspended, the subject will be directed to a specialist for a complete neurologic or musculoskeletal assessment. The identified neurologic or musculoskeletal abnormality is to be reported on the adverse **Events** CRF.

8.2.1.5 Physical Measurements

Height in centimeters should be measured without shoes. Weight in kilograms should be measured without shoes.

Waist circumference: Subjects should wear minimal clothing to ensure that the measuring tape is correctly positioned. Subjects should stand erect with the abdomen relaxed, arms at the sides, feet together and with their weight equally divided over both legs. To perform the waist measurement, the lowest rib margin is first located and marked. The iliac crest is then palpated in the midaxillary line, and also marked. It is recommended to apply an elastic tape horizontally midway between the lowest rib margin and the iliac crest, and tie firmly so that it stays in position around the abdomen about the level of the umbilicus. The elastic tape thus defines the level of the waist circumference, which can then be measured by positioning the measuring tape over the elastic tape. Subjects are asked to breathe normally, and to breathe out gently at the time of the measurement to prevent them from contracting their muscles or from holding their breath. Measurements should be performed using the same procedure throughout the study. The reading is taken to the nearest centimeter or 1/2 inch and entered in the source document.

8.2.2 Efficacy Assessments

Planned time points for all efficacy assessments are listed in the Schedule of Activities see ([Table 1-1](#)). Serum Lp(a), LDL-C, and ApoB will be collected with other clinical laboratory assessments described in Section [8.2.5](#).

8.2.3 Safety Assessments

Planned time points for all safety assessments are listed in the Schedule of Activities see ([Table 1-1](#)).

8.2.3.1 Vital Signs

The following measurements must be performed: systolic/diastolic blood pressure and heart rate. Subject must be in a supine position in a rested and calm state for at least 5 minutes before blood pressure assessments are conducted. If the subject is unable to be in the supine position, the subject should be in most recumbent position as possible.

The position selected for a subject should be the same that is used throughout the study and documented on the vital sign CRF. Record all measurements on the vital signs CRF.

8.2.3.2 Survival Status

Survival status should be obtained for all subjects within the limits of local law. This includes subjects who withdraws consent, or subjects considered lost to follow-up, or subjects unwilling to continue schedule of assessments and should include interrogation of medical, national, and public databases, if necessary. If deceased, the date and reported cause of death should be obtained.

8.2.3.3 Electrocardiograms (ECGs)

Subject must be in supine position in a rested and calm state for at least 5 minutes before ECG assessment is conducted. If the subject is unable to be in the supine position, the subject should be in most recumbent position as possible. The principal investigator designated site physician will review all ECGs. Once signed, the original ECG tracing will be retained with the subject's source documents. At the request of the sponsor, a copy of the original ECG will be made available to Amgen. Findings should be recorded on the ECG eCRF.

8.2.4 Adverse Events and Serious Adverse Events

8.2.4.1 Time Period and Frequency for Collecting and Reporting Safety Event Information

8.2.4.1.1 Adverse Events

The adverse event grading scale to be used for this study will be the Amgen Standard Grading Scale and is described in Section [11.4](#).

The investigator is responsible for ensuring that all adverse events observed by the investigator or reported by the subject that occur after enrollment through the **EOS** are reported using the Events CRF.

8.2.4.1.2 Serious Adverse Events

The investigator is responsible for ensuring that all serious adverse events observed by the investigator or reported by the subject that occur after signing of the informed consent through **EOS** are reported using the Events CRF.

All serious adverse events will be collected, recorded and reported to the sponsor or designee within 24 hours of the investigator's knowledge of the event, as indicated in

Section 11.4. The investigator will submit any updated serious adverse event data to the sponsor within 24 hours of it being available.

8.2.4.1.3 Serious Adverse Events After the Protocol-required Reporting Period

After EOS, there is no requirement to **actively** monitor study subjects **with regards to study subjects treated by the investigator**. **However**, if the investigator becomes aware of serious adverse events **suspected to be related to investigational product**, **then** these serious adverse events **will be** reported to Amgen within 24 hours following the investigator's awareness of the event **using the Serious Adverse Event Contingency Form**.

Serious adverse events reported outside of the protocol-required reporting period will be captured within the safety database as clinical trial cases and handled accordingly based on relationship to investigational product.

If further safety related data is needed to fulfill any regulatory reporting requirements for a reportable event, then additional information may need to be collected from the subject's records after the subject ends the study.

8.2.4.2 Method of Detecting Adverse Events and Serious Adverse Events

Care will be taken not to introduce bias when detecting adverse events and/or serious adverse events. Open-ended and non-leading verbal questioning of the subject is the preferred method to inquire about adverse event occurrence.

8.2.4.3 Follow-up of Adverse Events and Serious Adverse Events

After the initial adverse event/serious adverse event report, the investigator is required to proactively follow each subject at subsequent visits/contacts. All adverse events and serious adverse events will be followed until resolution, stabilization, until the event is otherwise explained, or the subject is lost to follow-up (as defined in Section 7.3). Further information on follow-up procedures is given in Section 11.4.

All new information for previously reported serious adverse events must be sent to Amgen within 24 hours following knowledge of the new information. If specifically requested, the investigator may need to provide additional follow-up information, such as discharge summaries, medical records, or extracts from the medical records. Information provided about the serious adverse event must be consistent with that recorded on the Events CRF.

8.2.4.4 Regulatory Reporting Requirements for Serious Adverse Events

If subject is permanently withdrawn from protocol-required therapies because of a serious adverse event, this information must be submitted to Amgen.

Prompt notification by the investigator to the sponsor of serious adverse events is essential so that legal obligations and ethical responsibilities towards the safety of subjects and the safety of a study treatment under clinical investigation are met.

The sponsor has a legal responsibility to notify both the local regulatory authority and other regulatory agencies about the safety of a study treatment under clinical investigation. The sponsor will comply with country-specific regulatory requirements relating to safety reporting to the regulatory authority, IRBs/IECs, and investigators.

Individual safety reports must be prepared for suspected unexpected serious adverse reactions according to local regulatory requirements and sponsor policy and forwarded to investigators as necessary.

An investigator who receives an individual safety report describing a serious adverse event or other specific safety information (eg, summary or listing of serious adverse events) from the sponsor will file it along with the Investigator's Brochure and will notify the IRB/IEC, if appropriate according to local requirements.

To comply with worldwide reporting regulations for serious adverse events, the treatment assignment of subjects who develop serious, unexpected, and related adverse events may be unblinded by Amgen before submission to regulatory authorities. Aggregate analyses may also be unblinded by the Safety Assessment Team, as appropriate. Investigators will receive notification of related serious adverse events reports sent to regulatory authorities in accordance with local requirements.

8.2.4.5 Safety Monitoring Plan

Subject safety will be routinely monitored as defined in Amgen's safety surveillance and signal management processes.

8.2.4.6 Pregnancy and Lactation

Details of all pregnancies and/or lactation in female subjects and pregnancy details for female partners of male subjects will be collected after the start of study treatment and until 90 days after receiving the last dose of study drug.

If a pregnancy is reported, the investigator is to inform Amgen within 24 hours of learning of the pregnancy and/or lactation and is to follow the procedures outlined in

Section 11.5. Amgen Global Patient Safety will follow-up with the investigator regarding additional information that may be requested.

Abnormal pregnancy outcomes (eg, spontaneous abortion, fetal death, stillbirth, congenital anomalies, and ectopic pregnancy) are considered serious adverse events.

Further details regarding pregnancy and lactation are provided in Section 11.5.

8.2.5 Clinical Laboratory Assessments

Refer to Section 11.2 for the list of clinical laboratory tests to be performed and to the Schedule of Activities (Table 1-1) for the timing and frequency.

The investigator is responsible for reviewing laboratory test results and recording any clinically relevant changes occurring during the study in the Events CRF. The investigator must determine whether an abnormal value in an individual study subject represents a clinically significant change from the subject's baseline values. In general, abnormal laboratory findings without clinical significance (based on the investigator's judgment) are not to be recorded as adverse events. However, laboratory value changes that require treatment or adjustment in current therapy are considered adverse events. Where applicable, clinical sequelae (not the laboratory abnormality) are to be recorded as the adverse event.

All protocol-required laboratory assessments, as defined in Section 11.2, must be conducted in accordance with the laboratory manual and the Schedule of Activities (Table 1-1).

Laboratory/analyte results that could unblind the study will not be reported to investigative sites or other blinded personnel until the study has been formally unblinded. In order to protect the blinding of the double-blind treatment period, the following labs will be blinded to the Amgen study team and site staff after day 1 until the study has been formally unblinded, and will not be reported to sites:

- Serum Lp(a)
- Lipid panel (see Appendix 2 Section 11.2 for a list of analytes)
- high sensitivity C-reactive protein (hs-CRP)
- **high sensitivity Interleukin 6 (hs-IL-6)**
- anti-olpasiran antibodies
- ApoA1
- ApoB

In addition, investigators and staff involved with this trial and all medical staff involved in the subject's medical care should not perform non-protocol testing of these analytes during a subject's study participation and until the end of the study, to prevent unblinding the patient and site to the treatment assignment, except when it is medically necessary. If a local lipid panel is drawn, all reasonable steps must be undertaken to avoid informing the subject and study personnel of the results.

If triglycerides are > 1000 mg/dL (11.3 mmol/L) at any scheduled assessment, the investigator will be informed, and a fasting triglyceride repeat test will be requested. If the retest confirms triglycerides > 1000 mg/dL (11.3 mmol/L), the Amgen medical monitor and the investigator will be informed so that appropriate medical follow up for the subject can be initiated.

Pregnancy Testing

A highly sensitive (serum) pregnancy test should be completed at screening and a screening urine pregnancy test should be completed the day of initiation of investigational product (prior to dosing) for females of childbearing potential.

Note: Females who have undergone a bilateral tubal ligation/occlusion should have pregnancy testing per protocol requirements. (If a female subject, or the partner of a male subject, becomes pregnant it must be reported on the Pregnancy Notification Form, see [Figure 11-2](#)). Refer to [Section 11.5](#) for contraceptive requirements.

Additional urine pregnancy testing should be performed prior to each administration of protocol-required therapies and 90 days after the last dose of investigational product. In the case of a positive urine result, a serum pregnancy test should be performed for confirmation.

Additional on-treatment pregnancy testing may be performed at the investigator's discretion or as required per local laws and regulations.

8.2.6 Pharmacokinetic Assessments

All subjects enrolled will have PK samples assessed.

Blood samples will be collected for measurement of serum concentrations of olpasiran as specified in the Schedule of Activities ([Table 1-1](#) and [Table 1-2](#)). Instructions for the collection and handling of biological samples will be provided by the sponsor. The actual date and time (24-hour clock time) of each sample will be recorded.

Drug concentration information that may unblind the study will not be reported to investigative sites or blinded personnel until the study has been unblinded.

8.2.6.1 Pharmacokinetic Sub-study

A PK sub-study will be conducted with a total of approximately 75 subjects (approximately 15 from each treatment cohort). A maximum of 3 samples may be collected at additional time points during the study if warranted and agreed upon between the investigator and the sponsor. Pharmacokinetic samples will be collected as per the PK sub-study schedule of assessments (see [Table 1-1](#) and [Table 1-2](#)).

8.2.7 Pharmacogenetic Assessments

If the subject consents to the optional pharmacogenetic portion of this study, DNA analyses may be performed. These optional pharmacogenetic analyses focus on inherited genetic variations to evaluate their possible correlation to the disease and/or responsiveness to the therapies used in this study. The goals of the optional studies include the use of genetic markers to help in the investigation of cardiovascular diseases and/or to identify subjects who may have positive or negative response to olpasiran. No additional samples are collected for this part of the study. For subjects who consent to this/these analysis/analyses, DNA may be extracted from residual cell pellets retained from selected biomarker plasma blood draws.

The final disposition of samples will be described in [Section 11.6](#).

8.2.8 Antibody Testing Procedures

Blood sample(s) for antibody testing are to be collected according to the time points specified in the Schedule of Activities ([Table 1-1](#)). Bioanalytical testing for anti-olpasiran antibodies will be conducted on these samples only if there are unexpected PD findings or antibody-related safety concerns in this study. Samples testing positive may be further characterized. Additional blood samples may be obtained to rule out anti-drug antibodies during the study.

Subjects who test positive for binding antibodies at the final antibody-scheduled time point and have clinical sequelae that are considered potentially related to an anti-olpasiran antibody response may also be asked to return for additional follow-up testing.

8.2.9 Biomarkers

Biomarkers are objectively measured and evaluated indicators of normal biologic processes, pathogenic processes, or pharmacologic responses to a therapeutic intervention.

8.2.9.1 Biomarker Assessment to Determine Eligibility

Blood Samples

For a subject to be eligible for study participation, a subject must have a Lp(a) value of > 150 nmol/L demonstrated during screening. Blood sample(s) need(s) to be collected after informed consent is obtained but prior to randomization. Screening for Lp(a) will be conducted using either an approved or investigational assay, investigational devices will follow regional regulatory requirements. The Lp(a) assay will be developed by Roche and screening will take place at a central laboratory as described in the Schedule of Activities ([Table 1-1](#)) and Appendix 2 (Section [11.2](#)).

8.2.9.2 Biomarker Assessment During the Study

Serum samples are to be collected for assessment of hs-CRP and hs-IL-6 at the time points specified in the Schedule of Activities ([Table 1-1](#)); however, the results of these biomarkers will not be included in the final clinical study report unless noteworthy.

Biomarker Discovery

Samples will also be collected for biomarker analysis, eg, to evaluate potential biomarkers that may correlate with treatment response.

Blood will be collected for biomarker discovery at the time points specified in the Schedule of Activities ([Table 1-1](#)), but results will not be reported in the final clinical study report.

Biomarker samples may include: oxidized phospholipids on apolipoprotein B-100 (OxPL/ApoB) and Lp(a) isoform size.

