
 • To evaluate the effect of olpasiran administered SC once every 24 weeks (Q24W) compared with olpasiran administered SC Q12W and placebo, on: 
 - percent change from baseline in Lp(a) - percent change from baseline in LDL-C - percent change from baseline in ApoB - achievement of Lp(a) < 125 nmol/L - achievement of Lp(a) < 100 nmol/L - achievement of Lp(a) < 75 nmol/L - achievement of Lp(a) < 50 nmol/L 	
For the olpasiran SC Q24W group:
 
 • Percent change from baseline at each scheduled visit, in: 
 - Lp(a) - LDL-C - ApoB • Achievement at each scheduled visit of the following: 
 - Lp(a) < 125 nmol/L - Lp(a) < 100 nmol/L - Lp(a) < 75 nmol/L - Lp(a) < 50 nmol/L

Objectives	Endpoints

Exploratory
	

 • To estimate cardiovascular event rates in subjects treated with olpasiran, including aggregated exploratory analyses across the olpasiran program 	
 • Adjudicated events

 • To describe the effect of olpasiran of quality of life (QoL) measures as assessed using the PROMIS Global Health 	
 • Change from baseline in PROMIS Global Health measures at each scheduled visit

 • To evaluate the effect of olpasiran administered SC on inflammatory biomarkers 	
 • Change from baseline at week 48 in: 
 - high sensitivity C-reactive protein (hs-CRP) - high sensitivity Interleukin 6 (hs-IL-6)

To assess the anti-olpasiran antibody response	
Anti-olpasiran antibody formation, if tested
Safety	

To evaluate the safety and tolerability of olpasiran administered SC compared with placebo in subjects with elevated Lp(a)	
Treatment emergent adverse eventsClinically significant safety laboratory values and vital signs at each scheduled visit

4. Study Design

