9.4.2 Methods of Analyses

9.4.2.1 General Considerations

Unless specified otherwise, efficacy analyses will be performed on the FAS by randomized treatment group, and safety analyses will be performed on the FAS by actual treatment group.

All categorical variables will be summarized using the number and percent of subjects and all continuous variables will be summarized using mean, standard error or standard deviation, median, minimum, maximum, and number of subjects with observations.

Analysis of exploratory endpoints will be specified in SAP.

Definition of Baseline Lp(a):

Baseline Lp(a) is defined as the mean of the two most recent non-missing Lp(a) values measured through central lab prior to or on study day 1. If for any reason only 1 value is available, then that value will be used as baseline.

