9.4.2.2 Efficacy Analyses

Endpoint	Statistical Analysis Methods
Primary	
The analysis of percent change from baseline in Lp(a) at week 36 will be performed when all randomized subjects have had the opportunity to complete the week 36 assessments or have early terminated. A repeated measures linear effects model including terms for treatment group, stratification factors, scheduled visit and the interaction of treatment with scheduled visit will be used. The least squares means (LS means) by treatment group and the treatment difference (olpasiran - placebo) based on the model above will be summarized. The Hochberg procedure will be used to control the type I error for multiple comparisons between active and placebo arms.
 
A sensitivity analysis will be performed using multiple imputation to impute missing data. Details of the imputation rules for the sensitivity analysis will be provided in the SAP.
 
Additional analysis of the primary endpoint will be explored using Multiple Comparison Procedure - Modelling (MCP-Mod) methodology (Bretz et al, 2005). Details will be provided in the SAP.

Secondary	
Analysis of the secondary endpoints will be performed when all randomized subjects have had opportunity to complete week 48 assessments or have early terminated.
 
Analysis of the secondary endpoints (including percent change from baseline at week 36 in ApoB and LDL-C, and percent change from baseline at week 48 in ApoB, Lp(a) and LDL-C) will be performed similarly to the analysis of the primary endpoint.

Exploratory	Will be described in the statistical analysis plan finalized before database lock

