9.4.2.3.2 Laboratory Test Results

The analyses of safety laboratory endpoints will include summary statistics at each scheduled visit by treatment group. Shifts in grades of select safety laboratory values between baseline and the maximum post-baseline grade will be tabulated by treatment group.

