9.1 General Considerations

Unless specified otherwise, efficacy analyses will be performed on the FAS by randomized treatment group, and safety analyses will be performed on the FAS by actual treatment group.

For the Primary Analysis (as described in Section 7.2), all data up to the primary analysis data cut-off date will be included. Based on the snapshot for the primary analysis, efficacy and safety analyses will be performed. Testing will be performed for endpoints defined up to week 36. Descriptive summary will be provided for all available visits by period (ie. Treatment period and extended safety follow-up period).

For the End of Treatment Period Analysis (as described in Section 7.3), all data up to the end of treatment period analysis cut-off date will be included. Testing will be performed for endpoints defined up to week 48. Descriptive summary will be provided for all available visits by period (ie. Treatment period and extended safety follow-up period).

For the Final analysis (as described in Section 7.4), all efficacy and safety analyses during the extended follow-up period will be performed based on the snapshot for the final analysis.

Subject disposition, demographics, baseline characteristics, and exposure to IP will be summarized.

All categorical variables will be summarized using the number and percent of subjects and all continuous variables will be summarized using mean, standard error or standard deviation, median, minimum, maximum, and number of subjects with observations.

Multiplicity Adjustment Method:

The Hochberg procedure will be used to control the type I error for multiple comparisons between active and placebo groups in the primary endpoint. The primary endpoint includes percent change in Lp(a) from baseline at week 36 for olpasiran SC Q12W groups and placebo. Percent change in Lp(a) from baseline for Q24W group is defined as exploratory endpoint.

A summary of the analyses for each planned analysis can be found in Table 2.

Table 2. Summary of Analyses

Analyses	Primary Analysis (all data up to primary analysis data cut-off date)	End of Treatment Period Analysis (all data up to End of Treatment Period Analysis data cut-off date)	Final Analysis (all data based on final snapshot)

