Efficacy	
 • Repeated measures model for primary endpoint, secondary endpoints defined at week 36, and exploratory endpoints of percent change from baseline in Lp(a), LDL-C and ApoB up to week 36. • Multiplicity adjustment for primary endpoint, as described above in Multiplicity Adjustment Method • Sensitivity analysis for primary endpoint using non-parametric (Quade test) approach based on CAS • Cochran-Mantel Haenszel (CMH) test adjusted by the stratification factors will be used for exploratory endpoints of Lp(a) achievements 	
 • Repeated measures model for primary endpoint, secondary endpoints defined at week 36 and week 48 and exploratory endpoints of percent change from baseline in Lp(a), LDL-C and ApoB up to week 48. Testing is performed up to week 48. • Multiplicity adjustment for primary endpoint, as described above in Multiplicity Adjustment Method • Sensitivity analysis for primary endpoint using non-parametric (Quade test) approach based on CAS • Cochran-Mantel Haenszel (CMH) test adjusted by the stratification factors will 	
 • Descriptive summary for efficacy endpoints in the extended follow-up period

	
(including achievement of Lp(a) < 125nmol/L) up to week 36
 
 • Descriptive summary for all efficacy endpoints by period (ie. Treatment period and extended safety follow-up period) 	
be used for exploratory endpoints of Lp(a) achievements (including achievement of Lp(a) < 125nmol/L) up to week 48
 
 • Descriptive summary for all efficacy endpoints by period (ie. Treatment period and extended safety follow-up period) 	
Safety	
 • Summary by actual treatment group by period (ie. Treatment period and extended safety follow-up period) 	
 • Summary by actual treatment group by period (ie. Treatment period and extended safety follow-up period) 	
 • Summary by actual treatment group in the extended follow-up period

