9.5.3 Analyses of Exploratory Efficacy Endpoint(s)

Exploratory endpoints of percent change from baseline at scheduled visits in Lp(a), LDL-C and ApoB will be analyzed using repeated measures linear effects model including terms for treatment group, stratification factors, scheduled visit and the interaction of treatment group with scheduled visit will be used; and achievements of Lp(a) at scheduled visits (including achievement of Lp(a) < 125nmol/L) will be analyzed using CMH test as specified in Table 2. Subject incidence of positively adjudicated events (overall and by event type as defined in protocol) and change from baseline in PROMIS Global Health measures at scheduled visits will be summarized by treatment group using descriptive statistics.

Descriptive summary for non-HDL-C, HDL-C, VLDL-C and Triglycerides will be provided by scheduled visits.

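### Whether the week 48 hs-CRP and hs-IL-6 endpoint enters the study report depends on its result, under a criterion the plan does not define

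*Protocol*

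**What the plan says.** Among the exploratory objectives in Protocol Section 3 and SAP 2.1 is this one: "To evaluate the effect of olpasiran administered SC on inflammatory biomarkers". The paired endpoint is the week 48 change in hs-CRP and hs-IL-6.

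Protocol 8.2.9.2 has serum collected for both markers at the visits in Table 1-1, but adds that "the results of these biomarkers will not be included in the final clinical study report unless noteworthy". Neither document gives a criterion, a decision-maker or a time for that judgement.

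The protocol does not specify exploratory analyses itself. Section 9.4.2.1 says "Analysis of exploratory endpoints will be specified in SAP", and the exploratory row of the table in 9.4.2.2 reads "Will be described in the statistical analysis plan finalized before database lock".

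SAP 9.5.3 covers percent change in Lp(a), LDL-C and ApoB, the Lp(a) thresholds, adjudicated events, PROMIS and four further lipid measures. It names neither inflammatory marker, and nor does SAP Table 2. For PROMIS, another exploratory change-from-baseline endpoint, the commitment is unconditional: "change from baseline in PROMIS Global Health measures at scheduled visits will be summarized by treatment group using descriptive statistics".

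**The concern.** The reporting rule is conditional on the data. If the week 48 results look unremarkable, the rule leaves them out of the final study report; if someone judges them striking, they go in. Because the threshold is undefined, nothing in the plan limits that judgement. It could also be made with treatment assignments known: under Protocol 9.4.1.3 the sponsor is unblinded after the end-of-treatment snapshot, which holds the week 48 data, and the final analysis comes later.

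A finding of no change would itself be informative. Protocol 2.3 names immune inflammatory response among the events of interest for this class of drug. If the report is silent, its reader cannot tell whether the markers were analysed and unremarkable or not analysed at all.

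**Working it through.** The documents give no figure to reproduce and no arithmetic applies. The check follows each marker through the two documents.

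| Where | hs-CRP | hs-IL-6 |
|---|---|---|
| Listed endpoint, week 48 change (Protocol 3, SAP 2.1) | yes | yes |
| Report only if noteworthy (Protocol 8.2.9.2) | yes | yes |
| Named analysis in SAP 9.5.3 or Table 2 | no | no |
| Chemistry analyte (Protocol Table 11-1) | yes, and also under biomarkers | no, biomarkers only |
| Column in SAP Appendix A | yes, with chemistry; week 48 is days (294, 420] | none |

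1. **Is the reporting rule result-dependent?** Yes. The same section offers a contrast: biomarker-discovery results are kept out of the final report without any condition. That exclusion is neutral to the result. The rule for hs-CRP and hs-IL-6 is not, and these two are the markers that have been made an endpoint.

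2. **Does the SAP supply the analysis that the protocol leaves to it?** Not by name, for either marker (0 of 2). The definitions needed are already there: SAP 5.2 takes the last non-missing value on or before Study Day 1 as baseline for such variables and defines change as a simple difference. Only the commitment to a summary is missing.

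3. **Does general text fill the gap?** Four statements might:
   - Protocol 9.4.2.3.2: "The analyses of safety laboratory endpoints will include summary statistics at each scheduled visit by treatment group".
   - SAP 9.6.2, which promises descriptive statistics for selected laboratory parameters without naming them.
   - SAP 9.1: "all continuous variables will be summarized using mean, standard error or standard deviation, median, minimum, maximum, and number of subjects with observations".
   - SAP Table 2: "Descriptive summary for all efficacy endpoints by period".

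   For hs-CRP the first two are plausible routes, since it is a chemistry analyte with a visit window. For hs-IL-6 they are not clear routes, because it is not listed as chemistry and has no window. The last two are broad enough to be read as covering either marker, but they name neither. None of the four commits to the week 48 change, and none clearly overrides the specific rule in Protocol 8.2.9.2.

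4. **Is the missing hs-IL-6 window a separate fault?** No. Appendix A covers selected endpoints that will be summarized descriptively. A marker with no planned summary needs no window, so its absence follows from the reporting rule.

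**The case against.** The strongest reply is that the rule is stated openly and in advance, and that the SAP follows it. The SAP's amendment history, which serves here only as context, records that biomarker language was taken out of 9.5.3 because of the protocol rule. This stands: the SAP's silence is deliberate and is a consequence of the rule, not an independent oversight. It does not remove the point, because stating a result-dependent rule in advance does not make it independent of the result. If the silence is intended, it is hard to see why the endpoint remains in both objectives tables.

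A second reply is that hs-CRP is probably summarized already as a safety laboratory value. That largely stands for hs-CRP. It does not carry over clearly to hs-IL-6.

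A third is that a reader who holds the protocol has an explanation for the markers' absence from the report. That is fair, and it makes the ambiguity small. It does not tell that reader what the data showed.

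Three stronger readings are tempting, and the documents do not support them:
- That neither marker will be analysed. The rule covers the final study report only and does not bar analysis, and general text may produce an hs-CRP table.
- That the lack of an hs-IL-6 window is a gap in its own right. It follows from the absence of a planned summary.
- That the number of subjects or samples measures the harm. Those counts describe volume; no estimate, error rate or conclusion depends on them.

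**Conclusion.** The point holds in a limited form. A listed exploratory endpoint is reported only if its result is judged noteworthy, by an unstated standard, and the SAP accordingly names no analysis of it. The gap is clearest for hs-IL-6; for hs-CRP a summary may already arise from the laboratory tables.

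Importance is low. No primary or secondary analysis is touched, and SAP 9.6.1 summarizes immune-inflammatory adverse events of interest without any such condition, so a clinical signal would still be visible. This is a cheap improvement. The conclusion rests on the current text of both documents and assumes no effect size, variability or drop-out rate.

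**What to change.** **Protocol 8.2.9.2.** Replace the whole clause about the final study report with a statement that week 48 results for hs-CRP and hs-IL-6 will be summarized descriptively in that report whatever they show. Striking only the last two words of the clause would be a mistake: the remaining sentence would say that the results are never included.

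**SAP 9.5.3 and Table 2.** Add, for each marker, a by-arm descriptive summary of baseline, week 48 and change from baseline, using the definitions in SAP 5.2 and the statistics in SAP 9.1.

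**SAP Appendix A.** As a consequence, add hs-IL-6 to one of the columns.

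**Alternative.** If the sponsor does not intend to report the markers, remove the endpoint from Protocol Section 3 and SAP 2.1 by amendment. SAP Section 10 then needs no entry, since the SAP would not depart from the amended protocol. Merely defining noteworthy and naming who decides before unblinding would limit discretion, but reporting would still depend on the result.

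**Cost.** For the main route: two descriptive tables, short SAP text, one Appendix A entry, and a minor protocol wording amendment with the IRB/IEC submission described in Protocol 11.3. No new samples are needed, because the Schedule of Activities already includes both markers. The alternative needs no tables but also requires a protocol amendment.
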